2 INTRODUCTION

2.1 Study Rationale

Malaria is a mosquito-borne protozoan disease belonging to the genus *Plasmodium* that affects approximately 219 million people and kills approximately 435,000 individuals annually, with an enormous economic impact in the developing world, especially sub-Saharan Africa. The 5 recognized species of *Plasmodium* that cause human malaria infection are Pf, P. vivax, P. ovale, P. malariae, and P. knowlesi. Among these, Pf causes more deaths in children worldwide than any other single infectious agent. An estimated 30,000 travelers from North America, Europe, and Japan contract malaria per year. Although malaria is preventable with chemoprophylaxis and completely curable with early intervention, drug treatment is not readily accessible in many parts of the world. Additionally, the use of antimalarial drugs over time has been associated with the emergence of drug-resistant strains. Lack of compliance with preventive drug treatment by individuals travelling to endemic areas may also result in fatal malaria infection. The world's first malaria vaccine, RTS,S/AS01 (MosquirixTM), a recombinant protein-based vaccine targeting Pf, was approved for use by European regulatory authorities in 2015. RTS,S/AS01 is currently being evaluated in an ongoing pilot immunization program in sub-Saharan Africa despite having been found to provide only partial protection against malaria to children and infants.^{2,3} Based on results from the ongoing pilot program, the World Health Organization (WHO) recently recommended widespread use of RTS,S/AS01 in a schedule of 4 doses in infants from 5 months of age in sub-Saharan Africa and in other regions with moderate to high Pf malaria transmission. ⁴ Therefore, the development of safe and effective malaria vaccines or protective antibodies for complete prevention and ultimate elimination of malaria remains an urgent unmet medical need with the potential to have a major impact on improving public health worldwide.

2.1.1 Year 2 Extension

The primary objectives of the protocol extension are to assess the safety and PK of a second dose of L9LS in children exposed to seasonal malaria transmission in Mali. There are several potential clinical use cases for anti-malarial MAbs that may involve repeated administrations of the same MAb to the same individual. For example, the WHO currently recommends repeated, intermittent (e.g., monthly) courses of chemoprevention for high-risk groups such as children under 5 years of age exposed to seasonal malaria, and pregnant women. Although chemoprevention is a critically important tool, its effectiveness may be limited by the challenge of delivering frequent treatment courses, and the emergence of drug resistance. A single dose of a monoclonal antibody that prevents infection for up to 6 months could be administered before each malaria season for at-risk children and in early pregnancy, complementing chemoprevention and other malaria control measures. Therefore, it is important to assess the safety and PK of repeated dosing of L9LS in target populations such as children exposed to seasonal malaria who could receive annual dosing of an anti-malaria MAb before each malaria season. In addition, the study extension offers the opportunity to explore the efficacy of a second

Version Date: 14 March 2024

dose of L9LS (first exploratory objective), to explore the risk of 'rebound' malaria in children who received L9LS in the first year of the study but not in the second year (third exploratory objective), and to explore the relationship between the PK of L9LS and the risk of Pf infection and clinical malaria (fourth and fifth exploratory objectives, respectively).

2.2 Background

2.2.1 Study Agent: L9LS

2.2.1.1 Development

L9, the wild-type parent of L9LS, was isolated by sorting the Pf circumsporozoite protein (CSP)-reactive memory B cells obtained from a subject immunized with a radiation-attenuated Pf whole-sporozoite malaria vaccine in the VRC 314 clinical trial (NCT02015091) using a junctional epitope mimic probe designed to select for "CIS43-like" MAbs. Epitope mapping showed L9 bound to NPNV motifs associated with NVDP minor repeats of PfCSP. When compared to a published panel of protective human PfCSP MAbs, L9 protected mice against IV and mosquito bite sporozoite challenge, and demonstrated the lowest ED80 and EC80 values (325.7 μ g and 145.1 μ g/mL, respectively) of any MAb evaluated, including CIS43LS (685.92 μ g and 363.93 μ g/mL, respectively). ¹¹ The unique preference of L9 for NPNV motifs was further underscored by the fact that all four NVDP tetrapeptide motifs had to be mutated to NANP to disrupt the recognition of L9 for the NPNV motifs found in recombinant PfCSP. As 100% of known Pf field isolates have one or more NVDP motifs, these data suggest that L9 should bind all circulating strains of Pf malaria. ¹¹

Half-life extension of L9 was accomplished by modifying the L9 Fc heavy chain to include a LS mutation (L9LS). Restriction enzymes were used to digest plasmids carrying the L9 heavy chain and the CIS43LS heavy chain; subsequently, the variable region of the L9 heavy chain was

Version Date: 14 March 2024

ligated to the Fc heavy chain bearing the LS mutation. The LS mutation is a methionine to leucine (L) and asparagine to serine (S) (M432L/N434S, collectively, LS) replacement, and changes have been reported to increase antibody Fc region binding affinity to FcRn, resulting in the extended recirculation of functional IgG and consequent longer antibody serum half-life. Other than these two amino acid sequences in the heavy chain Fc, the sequences of L9LS and L9 are identical. Immune protection and half-life data acquired with L9 and L9LS identify L9LS as a promising clinical candidate for passive malaria prophylaxis.

2.2.1.2 Preclinical Experience

To assess L9LS as a candidate for clinical trials, research-grade MAb was evaluated for in vitro functional activity including binding properties, auto-reactivity, and PK, and in mouse models of in vivo protection following challenge. In addition, PK studies in non-human primates (NHPs) were performed. In mice, L9 was more potent than CIS43, and both L9LS and L9 mediated the same potency following challenge. In NHP PK studies, L9LS exhibited significantly longer half-life in blood as compared to the parental L9 MAb without the LS mutation.

Two preclinical toxicology studies were conducted with a process-representative developmental batch of L9LS. An in vitro tissue cross-reactivity (TCR) assay to screen for potential cross-reactivity and an in vivo rat toxicity study to demonstrate safety both were conducted in compliance with 21 CFR 58 Good Laboratory Practice (GLP) for Nonclinical Laboratory Studies.

2.2.1.2.1 TCR Study

The TCR assay screened a standard panel of normal human tissues (three donors per tissue) and Sprague Dawley rat tissues (two rats per tissue). Mammalian cells transfected to express CSP were used as a tissue-positive control. Two concentrations of L9LS were tested: $1.15 \,\mu g/mL$ (selected as the concentration which saturated the positive control tissue), and $11.5 \,\mu g/mL$ (10-fold excess). A negative control IgG1 κ antibody (GR338422-1, no mammalian target antigen) was tested at the same two concentrations. L9LS exhibited scattered specific membrane binding in 3/3 human salivary gland tissue samples and localized to the epithelial cells lining the ducts and acini. Binding was rare (1-5% of these epithelial cells) at $1.15 \,\mu g/mL$, and rare to occasional (5-25% of these epithelial cells) at $11.5 \,\mu g/mL$. The cause of the salivary epithelial cell membrane binding has not been identified. Specific membrane binding to salivary gland tissue was not observed for the negative control antibody. L9LS did not bind to rat salivary epithelium. No specific membrane binding to other human tissues was observed.

2.2.1.2.2 Rat Toxicity Study

Sprague Dawley rats were dosed with L9LS to evaluate toxicity and toxicokinetics. Rats received 0, 40, or 400 mg/kg by IV bolus injection twice (Day 1 and Day 11). Female rats were dosed with 10 mg/kg by SC injection once (D1); male rats were dosed with 10 mg/kg SC twice (D1 and D11); both male and female rats were dosed with 100 mg/kg SC twice (Day 1 and Day

Version Date: 14 March 2024

11). For all dose levels, the main group was necropsied at Day 12 to evaluate potential immediate effects, and recovery animals were necropsied at Day 46, to evaluate the potential for delayed effects and recovery. Treated rats exhibited a transient increase in body temperature post-dose (up to + 0.5°C, considered a non-adverse response). Serum clinical chemistry tests detected slightly increased globulin, consistent with the administration of L9LS, an IgG MAb. For IV dosing, the no observed adverse effect level (NOAEL) was the high dose, 400 mg/kg IV x2. For SC dosing, the NOAEL was the high-dose, 100 mg/kg SC x2. SC injection of L9LS did not cause reactogenicity (edema, erythema, eschar) in any rat. Histopathology evaluation of the skin at the SC injection site reported minimal to moderate SC mixed cell infiltration, considered treatment related and predictive for human volunteers. One treated rat (in the 100 mg/kg SC group) was found dead; this event was attributed to a procedural error the previous day and is not considered treatment related. One treated female (in the 100 mg/kg SC recovery group, n=30) had grossly visible heart enlargement (2-fold increase in both heart weight and heart-body weight compared to the control means), with normal heart histology. Spontaneous cardiomyopathies are occasionally observed for the Sprague Dawley strain of rat. Based on the singular incidence, this observation is not considered treatment related.

With reference to the US Food and Drug Administration (FDA) Center for Drug Evaluation and Research 2005 Guidance for Industry Estimating the Maximum Safe Starting Dose in Initial Clinical Trials for Therapeutics in Adult Healthy Volunteers, scaling based on body weight is appropriate for a MAb expected to distribute mainly in the vascular space. The rat IV NOAEL of 400 mg/kg x2 supports the IV clinical high dose with a 20-fold dose margin. The rat SC NOAEL of 100 mg/kg x2 supports the SC clinical dose with a 20-fold dose margin.

The FDA provides guidance on "the nonclinical safety studies recommended to support human clinical trials" in the Guidances for Industry ICH M3(R2) Nonclinical Safety Studies for the Conduct of Human Clinical Trials and Marketing Authorization for Pharmaceuticals and ICH S6 Addendum to Preclinical Safety Evaluation of Biotechnology-Derived Pharmaceuticals. Taken together, the L9LS TCR and rat toxicity study results meet the safety standard set in these guidances and support proceeding with L9LS clinical trials.

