The year 2 extension phase will include only participants who are currently enrolled in the study and agree to continue in the extension.

Version Date: 14 March 2024

Phase: 2

Description of Sites/Facilities Enrolling Participants:

The MRTC clinics in Kalifabougou and Torodo. All screening, day 0 (study agent administration), and day 14 visits will be performed at Kalifabougou only. Both sites will conduct recruitment, enrollment, follow-up visits (other than day 14 as noted above), and unscheduled

study visits.

For the year 2 extension phase, all day 0 (study agent administration) will be performed at Kalifabougou only. Both sites (Kalifabougou and Torodo) will conduct recruitment, enrollment, follow-up visits, and unscheduled study visits.

Description of Study Intervention:

The study agent will be administered as a one-time SC injection or IV infusion as follows: L9LS at a dose of 150 mg SC (children only), 300 mg SC (children and adults), 600 mg SC (adults only), or 20 mg/kg IV (adults only), or matching placebo (children only).

In the year 2 extension phase, the study agent will be administered as a one-time SC injection as follows: L9LS at a dose of 150 mg or 300 mg, or matching placebo.

Study Duration:

36 months.

Participant Duration:

7 months for dose escalation subjects (plus 2 months for those in the pediatric dose-escalation cohort who agree to additional follow-up visits, see Appendix E); 6 months for efficacy subjects.

Year 2 extension phase: 12 months from the time of enrollment in the extension.

Version Date: 14 March 2024

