2.2.1.3 Clinical Experience

The first generation anti-malaria MAb CIS43LS was shown to be safe and conferred complete protection against experimental controlled human malaria infections (CHMI) in a phase 1 study in healthy adult volunteers at the VRC. ¹⁰ In the phase 1 study, subjects were protected against malaria infection when challenged in CHMI at about 4 weeks to 36 weeks post-product administration. As noted above, a phase 2 trial involving healthy adults in Mali demonstrated the safety and protective efficacy of a single IV infusion of CIS43LS at doses of 10 mg/kg or 40 mg/kg. By time-to-event analysis, compared to placebo at 6 months, CIS43LS efficacy was 88.2% (adjusted 95% CI, 79.3 to 93.3; P<0.0001) for 40 mg/kg, and 75.0% (adjusted 95% CI, 61.0 to 84.0; P<0.0001) for 10 mg/kg (Kayentao et al. *N Engl J Med, In press*; ClinicalTrials.gov

Version Date: 14 March 2024

Identifier: NCT04329104; FMOS/FAPH Protocol Number: 2020/32/CE/FMOS/FAPH). Together, the phase 1 and 2 trials of CIS43LS provide proof of concept that a MAb with an extended half-life can safely confer protection against Pf infection.

L9LS was recently evaluated in a phase 1, dose-escalation, open-label clinical trial with CHMI to evaluate safety and protective efficacy in healthy, malaria-naive adults at the VRC (ClinicalTrials.gov Identifier: NCT05019729). The trial was a two-part, dose-escalation, adaptive-design study evaluating the safety, tolerability, PK, and protective efficacy of L9LS. Doses evaluated ranged from 1 to 20 mg/kg delivered via IV administration, and 5 mg/kg delivered via SC administration. No safety concerns were identified. A total of 17 L9LS recipients and 6 control participants underwent CHMI. Of the 17 participants who received a single dose of L9LS, 15 (88%) were protected after CHMI. Parasitemia did not develop in any of the participants who received 5 or 20 mg/kg of IV L9LS. Parasitemia developed in 1 of 5 participants who received 1 mg/kg IV, 1 of 5 participants who received 5 mg/kg SC, and all 6 control participants through 21 days after CHMI. Protection conferred by L9LS was seen at serum concentrations as low as 9.2 μg/mL. Thus, in this small phase 1 trial, L9LS administered IV or SC protected recipients against malaria after controlled infection, without evident safety concerns, and all IV and SC administrations were well tolerated.¹²

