2.3 Risk/Benefit Assessment

2.3.1 Known Potential Risks

Risks of L9LS: As noted above, a similar malaria antibody, CIS43LS, was evaluated as safe and well tolerated, both in the VRC phase 1 study involving US adults, ¹⁰ and in the phase 2 trial involving adults in Mali (Kayentao et al. *N Engl J Med, In press*). Similarly, no significant safety concerns were evident following administration of L9LS in a dose range of 1 mg/kg to 20 mg/kg IV and 5 mg/kg SC in the VRC phase 1 study involving US adults. ¹²

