4.3 Justification for Dose

The doses used in this study were selected based on preclinical data and data generated in the ongoing phase 1 VRC study, which tested the dose range included in this protocol. This study will test fixed doses of L9LS in children in a defined range of subject weights to approximate the weight-based dosing used in the phase 1 VRC study. Compared to weight-based dosing, fixed dosing will provide a greater range of antibody concentrations in vivo for determining a protective L9LS titer. Fixed dosing is also simpler to administer, reduces the risk of medication errors, and is generally more cost effective—factors that are relevant to the potential use of L9LS in malaria-endemic regions.

Version Date: 14 March 2024

In the safety study, subjects aged ≥18 years weighing 60 kg or less will receive a SC dose of 300 mg (2 mL) or 600 mg (4 mL), approximating the weight-based dosing of 5 mg/kg and 10 mg/kg, respectively, in a 60-kg adult. An additional group of subjects aged ≥18 years weighing 60 kg or less in the safety study will receive an IV dose of 20 mg/kg. This dose will be administered IV rather than SC because 4 mL is the maximum volume of L9LS that will be administered SC in this study. In Kalifabougou, the average weight of adult females and males is 55.6 kg and 61.7 kg, respectively. In the safety and efficacy studies, subjects aged 6-10 years weighing ≥15 kg and ≤30 kg will receive a dose of 150 mg or 300 mg SC, approximating the weight-based dosing of 5 mg/kg and 10 mg/kg, respectively, in a 30-kg child, and 10 mg/kg and 20 mg/kg, respectively, in a 15-kg child. Based on recent data from the study site, approximately 85% of children aged 6-10 years in Kalifabougou weigh between 15 kg and 30 kg. The doses used in the efficacy study will complement the data generated in the ongoing phase 1 VRC study. The doses used in the phase 1 VRC study were derived from 1) efficacy data from the challenge studies performed in mice showing that the protective concentration of antibody in vivo is between 5-100 µg/mL in 2 different mouse models of malaria infection; 11 and 2) PK data from nonhuman primate studies with L9LS and prior clinical experience in healthy adults with human MAbs targeting HIV (i.e., VRC01, VRC01LS, and VRC07-523LS) and ebolavirus (MAb114) at the same dose.

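### Does the 20-fold subcutaneous margin in the rat toxicity section overstate the margin for this trial's higher SC doses?

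*Combined protocol and SAP*

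**What the plan says.** Section 2.2.1.2.2 scales from rat to human by body weight and gives one margin per route. For IV: "The rat IV NOAEL of 400 mg/kg x2 supports the IV clinical high dose with a 20-fold dose margin". For SC: "The rat SC NOAEL of 100 mg/kg x2 supports the SC clinical dose with a 20-fold dose margin". The SC no-effect level was the top SC dose tested: "For SC dosing, the NOAEL was the high-dose, 100 mg/kg SC x2".

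Section 2.2.1.3 describes the phase 1 trial in malaria-naive adults: "Doses evaluated ranged from 1 to 20 mg/kg delivered via IV administration, and 5 mg/kg delivered via SC administration". Section 2.3.1 repeats that range.

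This trial differs. The Synopsis lists three fixed SC dose levels (150, 300 and 600 mg) and one IV dose (20 mg/kg). Section 4.3 converts the fixed doses to mg/kg. For adults on 300 or 600 mg, they are described as "approximating the weight-based dosing of 5 mg/kg and 10 mg/kg, respectively, in a 60-kg adult". For children on 150 or 300 mg, they are 5 and 10 mg/kg at 30 kg, "and 10 mg/kg and 20 mg/kg, respectively, in a 15-kg child". Section 5.2 limits year-1 weight to 15 to 30 kg in children and to at most 60 kg in adults.

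**The concern.** The SC sentence speaks of a single clinical dose, but this trial has three SC dose levels, given to people whose weights vary. A reader could take 20-fold as the SC margin for the present trial. For most of its SC dosing that would be too favourable, because 5 mg/kg is the lowest year-1 SC exposure and 20 mg/kg the highest.

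The visible text offers no other SC-route margin, and SC is the only route used in children. Section 4.3 adds to the difficulty by saying that phase 1 covered this protocol's dose range. By route that is true only of IV, since SC was tested at 5 mg/kg alone. Taken together, the two sections could suggest that the higher SC doses have both a 20-fold SC margin and earlier SC exposure in humans. At stake is the accuracy of the nonclinical safety background in a paediatric protocol.

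**Working it through.** **Inputs.** Rat no-effect levels per administration: 400 mg/kg IV and 100 mg/kg SC (Section 2.2.1.2.2). Phase 1 doses: up to 20 mg/kg IV, and 5 mg/kg SC (Section 2.2.1.3). This trial's doses and weights: Sections 4.3 and 5.2. Planned numbers: Table 1.

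**Formula.** Margin = rat no-effect level (mg/kg) / human dose (mg/kg).

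**Reproducing the plan's figures.**
- IV: 400/20 = 20-fold, as printed.
- SC: 100/5 = 20-fold, as printed, with a human dose of 5 mg/kg.
- Counting both rat doses instead gives 800/20 = 40-fold for IV, which contradicts the printed value. The convention is therefore per administration.

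**SC-route ratio at this trial's year-1 doses**, 100 / (mg dose / kg weight):

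| Dose and weight | mg/kg | SC-route ratio |
|---|---|---|
| Child 150 mg, 30 kg | 5 | 20 |
| Child 150 mg, 15 kg | 10 | 10 |
| Child 300 mg, 30 kg | 10 | 10 |
| Child 300 mg, 15 kg | 20 | 5 |
| Adult 300 mg, 60 kg | 5 | 20 |
| Adult 600 mg, 60 kg | 10 | 10 |

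Adults lighter than 60 kg have somewhat lower ratios. At 55.6 kg, the site's mean female weight, 600 mg is 10.79 mg/kg and the ratio is 9.27.

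**People concerned.** Planned year-1 SC recipients of L9LS: adults 6 + 6 = 12; children 9 + 75 on 150 mg and 9 + 75 on 300 mg = 168; total 180. Arms where the ratio is at most 10-fold: 84 children on 300 mg and 6 adults on 600 mg, that is 90/180 = 50%.

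**Which trial does the sentence describe?**
- The paragraph opens with FDA guidance on a safe starting dose for first trials in healthy adults.
- Its IV sentence refers to a high dose, which implies several IV doses. Phase 1 had a range of 1 to 20 mg/kg; this trial has one IV dose.
- Its SC sentence refers to one dose. Phase 1 had one SC dose; this trial has three levels.
- Both printed ratios match phase 1 exactly.

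All four cues point to phase 1, though none is conclusive.

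**Systemic margin at the highest SC exposure.** 400/20 = 20-fold at 20 mg/kg, if systemic exposure after SC dosing does not exceed that after IV dosing at equal mg/kg.

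**The case for a change.** The strongest case for a change is that the same clarification is needed on either reading. If the sentence describes phase 1, the visible protocol gives no SC-route ratio for its own higher doses. If it describes this trial, 20-fold is too favourable for every exposure above 5 mg/kg. The gap is not marginal: 28 children (25 in the efficacy study, 3 in dose escalation) are planned on 300 mg in the 15 to 19 kg stratum, where the ratio lies between 5 and about 6.3 (100 × 19/300). The IV margin also does not cover injection-site effects, and the rat study found treatment-related cell infiltration at the SC site that it considered predictive for humans. The repair costs one or two sentences.

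The arithmetic and the lack of a named dose stand. So does the point that Section 4.3 is loose about route. The consequence does not follow, for four reasons.

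- Nothing in Section 2.2.1.2.2 conflicts with Section 4.3. One gives a ratio, the other gives doses in mg/kg, and a reader who wants the ratio at another dose can divide.
- Section 4.3 rests the doses on mouse protection data, primate pharmacokinetics, phase 1 data and earlier experience with other antibodies. It relies on no fold-margin.
- Whole-body mg/kg is a poor guide to local exposure. A 15-kg and a 30-kg child on 300 mg receive the same two 1-mL injections (Section 6.2.4), yet the metric gives them 5-fold and 10-fold.
- Section 4.1 has children dosed only after day-7 review of adults given 600 mg SC and 20 mg/kg IV. Dosing then goes from 150 to 300 mg and from heavier to lighter children, with an interim safety evaluation before the efficacy study.

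**Conclusion.** No change is called for. The 20-fold SC figure is arithmetically right for 5 mg/kg and most plausibly refers to the single SC dose of phase 1. What is missing is a label in a background section. The unstated ratios are 10-fold at 10 mg/kg and 5-fold at 20 mg/kg. They measure distance to the highest SC dose tested, at which no adverse effect level had been reached, and not to an observed toxicity. Supplying them would alter no dose, safety rule, endpoint, analysis or conclusion.

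This rests on three things. The phase 1 reading is well supported by the wording but not proven. On the other reading the sentence would be too favourable above 5 mg/kg, but the dose justification still would not depend on it. The systemic margin of 20-fold at 20 mg/kg assumes that SC exposure does not exceed IV exposure at equal mg/kg. The figures cover year 1 only, because the year-2 exclusion criteria in Section 5.2.1 set no weight limit. The investigator's brochure and part of Section 2.3.1 could not be seen, so the absence of an SC-route ratio is established only for the visible text. Nothing here says that any margin is inadequate or that any dose should differ.
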